RNA extracted from skin biopsies collected before and after *in vivo* treatment with apremilast (as detailed above) will be subjected to RNA sequencing. Illumina strand-specific TruSeq libraries will be prepared from the polyA selected RNA and subjected to 1x100 base sequencing on an Illumina HiSeq2500 machine. The number of samples proposed here (10 samples before treatment and 10 samples after treatment) is expected to yield sufficient statistical power for this approach; smaller numbers have been used in similar approaches to investigate drugs' mechanism of action (usually three samples).^[7-9]

RNA-seq analysis will be performed in conjunction with the Tulane Cancer Crusaders Next Generation Sequence Analysis Core (Tulane Cancer Center - <https://tulane.edu/som/cancer/research/core-facilities/cancer-crusaders/>). Gene and isoform expression will be determined using RSEM^[10] and differential expression will be analyzed using EB-seq.^[11] Genes that are identified as differentially expressed between the two groups with a False Discovery Rate (FDR) of < 0.05 will be subjected to analysis by *Ingenuity* (IPA, Redwood City, CA). This analysis will group the identified genes into specific pathways, cell types, or disease process. A similar approach will be conducted using *Gene Set Enrichment Analysis (GSEA)*. These experiments and GEP analysis will be performed in conjunction with our collaborator's ([name]) lab, given his extensive experience in this field.^[12, 13]

b. Protein analysis

Information identified by Ingenuity or GSEA (signaling pathways, regulatory molecules, etc...) will be verified using IHC staining on select samples.

IV. OBJECTIVES AND ENDPOINTS

1.Primary Objective Description

To determine the overall response rate (ORR) of apremilast in cutaneous disease of patients with recalcitrant dermatomyositis at 3 months.

The ORR will be measured using the Cutaneous Dermatomyositis Activity and Severity Index (CDASI) at months 0, 1, and 3.

CDASI is a validated tool to measure skin disease activity in dermatomyositis.^[14] ORR includes partial and complete responses. Complete response is defined by a CDASI score of zero. Partial response is defined by a decrease of CDASI score of at least 4 points. Calculation is performed as the CDASI score at 1, and 3 month(s) minus the score at baseline.

All investigators (PI and Sub-Is) will be trained on how to screen the patients per the CDASI score tool.

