Photograph of skin rash will be taken at months 0,1 and 3 and compared to baseline.

2. Secondary Objective(s) Description

To determine the durability of responses for up to 6 months on apremilast for responders at 3 months. The durability of responses includes partial and complete response durability. The durability of response will be measured using the CDASI at 6 months minus CDASI at 3 months. Complete response durability is defined as zero or minus difference between CDASI score at 6 months and CDASI score at 3 months. Partial response is defined as >4 points difference between CDASI score at 6 months and CDASI score at 3 months.

We will assess the response of all patients at 6 months to identify possible delayed response. Complete response is defined by a CDASI score of zero at 6 months. Partial response is defined by a decrease of CDASI score of at least 4 points at 6 months compared to baseline. Calculation is performed as the CDASI score at 6 month(s) minus the score at baseline.

Photograph of patient's rash will be taken at 6 months and compared to 3 months and baseline.

To determine the safety and toxicity of apremilast when administered at 30 mg twice daily in patients with dermatomyositis. The safety assessment will include the assessment of adverse events, serious adverse events, laboratory testing and physical examination.

An additional secondary endpoint will be to determine if patients who experience remission of their disease can be maintained on apremilast as monotherapy.

To determine the patient quality of life using the Dermatology Life Quality Index (DLQI)^[15] at baseline, 1, 3 and 6 months.

Patient will be assessed 1 month after discontinuing apremilast (follow up visit) to assess change in response post discontinuation of apremilast. Patients will be examined and, CDASI, MMT-8 and DLQI will be performed. Photograph of patient's rash will be taken. CBC, CMP, CK, aldolase and urine pregnancy test will be performed.

3. Exploratory Objectives:

We will measure muscle enzymes (creatin kinase (CK) and aldolase) at 0, 1, 3, and 6 month(s) of apremilast in patients with muscle disease.

We will assess disease activity using the manual muscle testing-8 (MMT-8) in patients with muscle disease.^[16]

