Skin biopsies from lesional skin will be performed before treatment with apremilast and after 3 months of treatment for gene expression profiling and IHC stain. IHC will be performed on the protein product of the genes showing the largest fold change from the RNA-sequencing.

All investigators (PI and Sub-Is) will be trained on how to screen the patients per the MMT-8 score tool.

V. STUDY ENROLLMENT AND TIMELINES

1. # of Patients Expected to Enroll: 10

2. Date of planned FSI: 04/02/2018

3. Date of planned LSI: 11/01/2018

4. Date of planned LSO: 05/01/2019

5. Patient treatment duration (# months): 6 months

6. Is an interim Analysis Planned? Yes

7. Date on planned Interim Analysis: 03/01/2019

8. Date of planned final report: 06/03/2019

9. Are patients reported outcomes measured: Yes

VI. STATISTICAL PLAN:

Results of the study will be analyzed using descriptive statistics:

- Proportion of patients with complete ORR at 1,3 months
- Proportion of patients with partial ORR at 1,3 months
- Proportion of patients with complete durability response at 6 months for the 3 months responders
- Proportion of patients with partial durability response at 6 months for the 3 months responders
- Proportion of patients with complete response at 6 months
- Proportion of patients with partial response at 6 months
- Mean change from baseline in muscle enzymes (CK and aldolase in patients with muscle disease)
- MMT-8 change will be calculated as mean change from baseline at 1,3 and 6 months
- DLQI change will be calculated by identifying the proportion of patients with minimal clinically important difference of at least 5 points.

Missing data will be handled using the last observation carried forward approach (LOCF).

GEP will be analyzed using inferential statistics with a False Discovery Rate (FDR) of < 0.05 .

VII. INFORMED CONSENT:

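### As written, partial durability counts CDASI rises of more than 4 points from month 3 to month 6, while rises above 0 and up to 4 points have no category

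*Combined protocol and SAP*

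**What the plan says.** Section IV.2 (Secondary Objectives) of the protocol gives the measure: "The durability of response will be measured using the CDASI at 6 months minus CDASI at 3 months". It names two categories: "The durability of responses includes partial and complete response durability". The first is defined by: "Complete response durability is defined as zero or minus difference between CDASI score at 6 months and CDASI score at 3 months". The second is defined by: "Partial response is defined as >4 points difference between CDASI score at 6 months and CDASI score at 3 months".

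Section VI (Statistical Plan) lists the resulting summary as "Proportion of patients with partial durability response at 6 months for the 3 months responders" and gives no other definition.

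Two neighbouring definitions show which direction is good. For the primary objective (Section IV.1): "Complete response is defined by a CDASI score of zero. Partial response is defined by a decrease of CDASI score of at least 4 points". For the month-6 assessment of all patients (Section IV.2): "Partial response is defined by a decrease of CDASI score of at least 4 points at 6 months compared to baseline". In both, a lower score is better.

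**The concern.** Durability should separate responders who hold their month-3 gain from those who lose it. Stability and further improvement already count as complete durability. If partial durability means a difference above 4 on the stated subtraction, it consists only of patients who got worse by more than 4 points, however much worse. Patients who worsened slightly appear in neither category. The order is therefore inverted: a rise of 5 counts as a form of durability and a rise of 1 does not.

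The partial-durability proportion could then include responders who have lost everything and omit responders who have kept most of their gain. A reader of the results would take it to mean the opposite.

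**Working it through.** The plan gives no figure to reproduce for this endpoint, so the check is an enumeration of the rules.

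**Inputs**
- d = CDASI(month 6) − CDASI(month 3); positive d is worsening (Sections IV.1 and IV.2).
- Complete durability: d ≤ 0. Partial durability: a difference above 4, with no direction word (Section IV.2).
- Population: month-3 responders. Let D = baseline − month 3. A partial responder has D ≥ 4. A complete responder (score 0) has D ≥ 5, because entry requires a CDASI of at least 5 (Section 8, Inclusion Criteria). So D ≥ 4 for every responder.
- Planned enrolment: 10 (Section V).
- Assumption: whole-point scores. No distribution of scores is assumed, since the documents give none.

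**Step 1. Classify each d under three readings of the partial rule**

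| Reading of partial | Complete only | Both | Partial only | No category |
|---|---|---|---|---|
| Signed, d > 4 | d ≤ 0 | none | d ≥ 5 | d = 1 to 4 |
| Absolute, \|d\| > 4 | d = −4 to 0 | d ≤ −5 | d ≥ 5 | d = 1 to 4 |
| Decrease, d < −4 | d = −4 to 0 | d ≤ −5 | none | every d ≥ 1 |

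The signed reading is the subtraction the protocol states. Rises of 1 to 4 have no category under any of the three. Wherever partial adds anything to complete, it adds only rises of 5 or more.

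**Step 2. Benefit kept, signed reading**

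Points kept = D − d. Scores are baseline/month 3/month 6.

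| Scores | D | d | Points kept | Category as written |
|---|---|---|---|---|
| 20/10/20 | 10 | +10 | 0 of 10 | partial durability |
| 20/10/12 | 10 | +2 | 8 of 10 | none |
| 30/10/16 | 20 | +6 | 14 of 20 | partial durability |
| 20/16/19 | 4 | +3 | 1 of 4 | none |

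The last two rows show that the rule does not always mislead: some patients it counts kept most of their gain, and some it omits lost most of theirs.

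More than half is kept when D − d > D/2, that is, d < D/2.
- Counted as partial (d ≥ 5): this requires D > 10. For D of 4 to 10, every patient counted has lost at least half of the month-3 gain.
- Unclassified (d = 1 to 4) with more than half kept: d = 1 at D = 4; d = 1–2 at D = 5–6; d = 1–3 at D = 7–8; all of d = 1–4 at D ≥ 9.

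**Step 3. Illustration with five invented responders**

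Scores: 20/10/8, 20/10/10, 20/10/12, 20/10/14, 20/10/20, so d = −2, 0, +2, +4, +10.
- As written: complete 2/5; partial 1/5 (the patient who lost all benefit); no category 2/5.
- If partial were a rise above 0 with its limit set at 4, for illustration only: partial is 1/5 if a rise of exactly 4 is lost, or 2/5 if it is partial.
- Still at least 4 points below baseline at month 6 (falls of 12, 10, 8, 6, 0): 4/5.

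**Step 4. Weight of one patient**

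One responder among R moves the proportion by 100/R points: 10 at R = 10, 12.5 at R = 8, 20 at R = 5, 33.3 at R = 3. R cannot exceed 10 at the planned enrolment, so the minimum is 10 points.

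**The case against.** The strongest reply is that the sentence has no direction word and the categories need not be exclusive. In the primary endpoint partial and complete response already nest: with entry CDASI of at least 5, anyone who reaches zero has also fallen by at least 4. Both other definitions of partial response are decreases, so this one might mean a further fall of more than 4. The nesting observation is right, but the reading does not rescue the rule. The signed result d > 4 follows from the stated subtraction without assuming exclusivity. The decrease reading would make partial durability stricter than complete durability, and it still gives small rises no category.

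A second reading splits durability by type of month-3 response, so that the d ≤ 0 rule governs complete responders only. A score of zero cannot fall, so the provision for a negative difference would then have no use, and the partial rule would remain unclear.

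It can also be said that Section VI does not claim the two proportions sum to 100%. True, but under the stated subtraction the trouble is the order: +5 counts and +2 does not.

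Finally, month-6 response against baseline is planned for all patients, so 20/10/20 would appear there as a non-responder and 20/10/12 as a partial responder. This limits the harm. That summary has another reference and population ("We will assess the response of all patients at 6 months to identify possible delayed response"), so it does not define durability among responders. Differing labels under it are not in themselves a contradiction.

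The point turns on one inequality sign, which is worth confirming in the source file; nothing in the text suggests it was misread.

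**Conclusion.** The concern holds. Under the protocol's own subtraction, partial durability is a CDASI rise of more than 4 points with no upper limit, and rises above 0 and up to 4 points are not classified. The gap remains under the signed, absolute and decrease readings. This is a stated rule that gives a wrong proportion, not a missing detail.

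The scope is narrow: one descriptive secondary proportion, on which no test or sample size depends. Month-3 ORR, complete durability and month-6 response against baseline are unaffected. How many patients would be misplaced cannot be said, because it depends on the size of the month-3 improvement, which the documents do not give. The score examples are illustrations and rest on whole-point scores. It should be fixed before analysis, because choosing a repair after seeing the data from at most 10 patients would be a post hoc decision.

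**What to change.** In Section IV.2, keep d ≤ 0 as complete durability. Restate partial durability as a rise above 0 and no larger than a stated limit, and add a third category, durability lost, for larger rises. The categories are then exclusive and exhaustive for month-3 responders. The sponsor should state the limit. If it is 4, the text must say whether a rise of exactly 4 is partial or lost: at the smallest response, 20/16/20 has d = 4 and no benefit left. Use the same wording in Section VI.

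The wording should also be reconciled with the progression definition in Section 7 (Brief Study Synopsis). That definition includes a 4-point CDASI rise, names no reference visit, and joins the rise to MMT-8 and DLQI worsening by an and. No change to that rule is proposed here.

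Categories based on d can still disagree with response against baseline. With the limit at 4, 20/16/18 is partial durability but only 2 points below baseline. Conversely, 20/10/14 (if 4 is lost) or 20/10/15 (if 4 is partial) is durability lost while still a month-6 responder. So also report, among month-3 responders, the proportion still at least 4 points below baseline at month 6, and summarise d as a continuous change.

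The cost is wording in two sections, one extra proportion and one continuous summary. CDASI is already scheduled at baseline, month 3 and month 6, so no new visits, patients or assessments are needed.

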We will add apremilast to their treatment regimen according to the approved dosage for psoriasis and psoriatic arthritis: 10 mg orally one time on day 1, 10 mg orally twice daily on day 2, 10 mg orally in

AM and 20 mg orally in PM on day 3, 20 mg orally twice daily on day 4, 20 mg orally in AM and 30 mg orally in PM on day 5, then 30 mg orally twice daily thereafter.

7. Brief Study Synopsis: With limited treatment options available for dermatomyositis, we hypothesize that apremilast, a phosphodiesterase-4 (PDE-4) inhibitor, is a safe and efficacious add-on treatment in patients with recalcitrant cutaneous dermatomyositis.

The study will investigate the efficacy, safety and toxicity of apremilast given at 30 mg twice daily to patients with recalcitrant cutaneous dermatomyositis. Clinical response will be assessed at 1 and 3 months. Patients will also be evaluated for durability of their response for up to 6 months.

Treatment will be monitored with frequent clinical visits (0, 1, 3 and 6 months) and blood tests (CBC, CMP, CK, aldolase). Treatment will be discontinued at disease progression or unacceptable adverse events. Disease progression is defined as a 4 points increase in CDASI score, worsening of muscle disease by MMT-8 score and 5 points increase in DLQI.

5 mm skin biopsies from lesional skin will be performed before treatment with apremilast and after 3 months of treatment for gene expression profiling and confirmatory immunohistochemical stains.

8. Inclusion Criteria:

- Must understand the risks and the benefits/purpose of the study and provide signed and dated informed consent.
- Must be 18 years at time of signing the informed consent form.
- Willing to participate in all required evaluations and procedures in the study including the ability to swallow pills without difficulty.
- Patients must have a diagnosis of DM based upon the characteristic cutaneous findings proposed by Sontheimer^[6] and/or a skin biopsy consistent with DM.
- Patients must be candidate for systemic therapy for their DM skin disease defined by inadequate response to aggressive sun protection along with the use of potent topical corticosteroids and/or immunomodulators.
- Patients with a diagnosis of dermatomyositis on steroid-sparing agent and/or systemic steroids (maximum dose of prednisone 1mg/Kg) and still having cutaneous disease activity of at least 5 on the CDASI scale.

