If the sequela of an overdose is an SAE, then the sequela must be reported on an SAE report form. The overdose resulting in the SAE should be identified as the cause of the event on the SAE report form but should not be reported as an SAE itself.

In the event of an overdose, the patient should be monitored as appropriate and should receive supportive measures as necessary. There is no known specific antidote for apremilast overdose. Actual treatment should depend on the severity of the clinical situation and the judgment and experience of the treating physician.

Overdose for this protocol, on a per dose basis, is defined as ingestion of any more than the amount prescribed of apremilast (or matching placebo) tablets in any 24 hour period whether by accident or intentionally.

IX. PATIENT'S WITHDRAWAL

The patient may withdraw from the study or withdrawn due to the many reasons:

- Loss to follow-up

- Adverse Event
- Non-Compliance
- Minimal/no therapeutic effect.
- Withdrawal of the patient by the investigator.
- Other reasons

Efforts should be made to follow-up patients with adverse events to know the final outcome of the event.

The patient and/or investigator, both have the right to terminate the patient's participation in the study. The reason for termination/withdrawal will be documented.

X. DATA MANAGEMENT

All data must be entered into the clinical data management system before initiating treatment. Electronic case report form (CRF) will be used for the collection of all study data entry at the clinical trial site. The PI will enter the data. All requested information must be entered in the CRF in a timely manner and the CRF for each visit must be completed during the visit. The completed CRF must be reviewed, signed and dated by the PI as well as any missing data should be recorded. Files containing electronic data will be password protected and encrypted and will be closed when computers are left unattended. Contact lists, recruitment records, or other documents that contain Protected Personally Identifiable Information (PPII) will be stored securely in locked cabinets or rooms and access to key codes will be limited.

XI. PUBLICATION PLAN

1.Target Journal: JAAD

2. If Other Specify: JAMA

3. Date of Planned manuscript: September 2019

XII. SUPPORT REQUESTED FROM CELEGENE RESOURCES

1. Requesting Study Drug? Yes

2. Requesting Study funding? Yes

3. Support Requested from other companies? No

4. Non-Celegene Support Sources: None

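### Unrestricted LOCF counts a responder whose last CDASI is the responding visit as a month-6 responder and, if the month-3 score is carried, as completely durable with no month-6 score

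*Combined protocol and SAP*

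**What the plan says.** Section IV.2 makes durability among month-3 responders, while taking apremilast, a secondary objective. It is measured as the month-6 CDASI minus the month-3 CDASI, and the best category is set by this rule: "Complete response durability is defined as zero or minus difference between CDASI score at 6 months and CDASI score at 3 months". The section then adds a second month-6 endpoint: "We will assess the response of all patients at 6 months to identify possible delayed response". Response there is a CDASI of 0, or a fall of at least 4 points from baseline.

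Section VI reports both as descriptive proportions, among them "Proportion of patients with complete durability response at 6 months for the 3 months responders" and "Proportion of patients with partial response at 6 months". Its missing-data rule is one sentence, with no exception by endpoint, visit or reason for leaving: "Missing data will be handled using the last observation carried forward approach (LOCF".

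Patients can stop early. The Brief Study Synopsis says: "Treatment will be discontinued at disease progression or unacceptable adverse events". Section IX adds loss to follow-up, adverse events, non-compliance and "Minimal/no therapeutic effect". For a patient who stops, the visit spelled out is in Section IV.2: "Patient will be assessed 1 month after discontinuing apremilast (follow up visit". CDASI is scored at that visit. The Schedule of Events has no CDASI between months 3 and 6. Nothing says that the month-6 CDASI is kept for a patient who has stopped drug, or which score LOCF should carry.

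**The concern.** Carrying the month-3 score into month 6 makes the durability difference zero by construction, and zero is enough for the best durability category. The missing visit itself then produces the favourable result. This comes from how the plan's own definition and its missing-data rule combine, and does not depend on a general objection to LOCF. The month-6 response proportion has a related problem: a score that met the response definition at the last visit still meets it when copied forward.

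The objective concerns response on apremilast. A responder who has left is not known to be responding at month 6 and may not be on drug. With no scheduled CDASI between months 3 and 6, a patient who relapses and is then lost can have the month-3 score as the last one. Descriptive proportions are the whole efficacy result, and no sensitivity analysis is planned that would reveal carried values.

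**Working it through.** The plan gives no dropout rate, expected response rate or power, so there is no figure to reproduce. From the documents: N = 10 (Section V), the response and durability definitions (Section IV), and LOCF (Section VI). The CDASI scores, the number of month-3 responders R3, and the number of departed responders L are assumptions. I leave the partial durability category aside, because its definition gives a size of difference but no sign.

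**1. Month-3 score carried.** Baseline 20, month 3 = 12, month 6 missing and set to 12.
- Durability difference: 12 − 12 = 0, so complete durability.
- Change from baseline: 12 − 20 = −8, so month-6 partial response.

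**2. Off-drug follow-up score carried instead.** Same patient, scored 18 one month after stopping.
- Durability difference: 18 − 12 = +6, so not complete durability.
- Change from baseline: 18 − 20 = −2, so no response.

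The classification thus turns on a choice that the plan does not make.

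**3. Month-1 responder who leaves before month 3.** Baseline 20, month 1 = 14, carried to months 3 and 6.
- Change from baseline: 14 − 20 = −6, a response in the primary month-3 ORR and again at month 6.
- Durability difference: 14 − 14 = 0, so the patient enters the durability denominator and counts as completely durable.

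**4. Size, LOCF against counting only observed responders.**
- Response proportions: L/10. L = 1 gives 10 points; L = 2 gives 20.
- Complete durability, month-3 responders who leave later: L/R3.

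| R3 (assumed) | L = 1 | L = 2 |
|---|---|---|
| 4 | 25.0 points | 50.0 points |
| 5 | 20.0 points | 40.0 points |
| 6 | 16.7 points | 33.3 points |

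A month-1 leaver, as in step 3, adds one to both numerator and denominator, so the durability shift is smaller. For example, 3/5 (60.0%) becomes 4/6 (66.7%).

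**5. Worked example (assumed).** Five of 10 respond at month 3. One of them is lost with the month-3 score as the last. The other 4 are seen and still respond against baseline, 3 of them with a difference of 0 or less. Of the 5 non-responders, 2 leave for lack of effect and 3 are seen without response.

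| Endpoint | LOCF | Observed over all | Not assessed | Bounds |
|---|---|---|---|---|
| Month-6 response | (4 + 1)/10 = 50% | 4/10 = 40% | 1 + 2 = 3 | 40% to 70% |
| Complete durability | (3 + 1)/5 = 80% | 3/5 = 60% | 1 | 60% to 80% |

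The 2 who left for lack of effect add nothing under either count.

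**The case against.** A reader might infer that every responder who leaves is counted as durable. The documents do not support that. Section IV.2 and the Schedule of Events provide a CDASI one month after stopping. Read literally, that could be the last observation, and a patient who stops at about month 5 would have it at about month 6. A patient stopped for progression should also have a worsened CDASI on record: the Synopsis definition includes a 4-point rise, and if that rise is measured from month 3 and the score is carried, the difference is at least +4, not 0. Both points stand, and they limit the claim to responders whose carried score is the responding visit. They do not remove it. A patient lost to follow-up has no later score, and if the follow-up score is used, an off-drug value stands in for response on apremilast.

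A reader might also infer that LOCF turns patients withdrawn for lack of effect into responders. It does not. A carried non-response stays a non-response, and the only loss is that a delayed response is not observed.

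The strongest objection is that the replacement may lie further from what would have been seen. Let q be the probability that a departed responder would not have met the status at month 6. LOCF overcounts by L × q on average; counting only observed responders undercounts by L × (1 − q). For assumed L = 1 to 2 and q = 0.2 to 0.5:
- Month-6 response: LOCF is off by 1 × 0.2/10 = 2 to 2 × 0.5/10 = 10 points; the observed count by 1 × 0.5/10 = 5 to 2 × 0.8/10 = 16 points.
- Durability, R3 = 6 to 4: LOCF is off by 1 × 0.2/6 = 3.3 to 2 × 0.5/4 = 25 points; the observed count by 1 × 0.5/6 = 8.3 to 2 × 0.8/4 = 40 points.

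The arithmetic is right: over this range the observed count is never closer, and the two are equal only at q = 0.5. It does not decide the matter, because the objective is response on apremilast, which a leaver has not been shown to have. An observed count with the number not assessed shows both bounds; a LOCF figure alone shows neither.

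It is also fair that the sentence on assessing all patients at month 6 is not itself at fault. It may express an intention to score everyone. The operative text is the LOCF rule in Section VI.

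**Conclusion.** The point holds in conditional form. When the responding visit supplies the carried score, LOCF counts an unseen patient as a month-6 responder, and when that score is the month-3 score, as completely durable. It also carries departed month-1 responders into the primary month-3 ORR. Where a follow-up or progression score exists, the outcome depends on a rule that the plan does not give.

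The overall size is unknown, since the documents give no dropout figure and R3 is assumed; with complete scoring there is no effect. Impact is minor to moderate: the analyses are descriptive, in 10 patients, with no test attached. Nor can it be said that carried values would be untraceable. Section IX documents reasons for withdrawal and Section X requires missing data to be recorded, so these patients can be identified. Section VI simply does not commit to showing them. The change is still worth making, because one patient can alter a reported proportion visibly and the remedy is cheap.

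**What to change.** In Section VI, replace LOCF for the CDASI response and durability proportions at months 3 and 6:
- **Response:** observed on-drug responders over all enrolled patients.
- **Durability:** patients observed on drug at month 6 who meet the category, over all observed month-3 responders.
- **Unobserved patients:** not counted as responders or as durable. Off-drug follow-up scores are reported separately and not used as on-drug response.
- **Display:** the number not assessed, with reasons, beside each proportion, so that the lower and upper bounds can be read off.

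Optionally, keep the scheduled CDASI visits for consenting patients who stop drug, with those scores labelled off-drug. They describe the patient's course but cannot show what continued treatment would have done.

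The cost is small: a change of text, a column in the tables and, if the option is taken, one or two already scheduled visits in the few patients who stop. The figures will be less favourable (in the example, 4/10 instead of 5/10 and 3/5 instead of 4/5). They are also conservative, because a leaver who would have kept the response is not credited. Patients' and investigators' rights to stop are unaffected.
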